APPENDIX I: POST-VISIT INTERVIEW QUESTIONS

1. How would you describe your experience with the CGM to someone else?
2. Can you please list the top 3 things you liked about the CGM?
3. What did you not like about it?
4. How did wearing the CGM feel?
5. When would you look at your device typically?
6. If I wanted to check my historic glucose readings, where would I look? How would I interpret this?
7. If I wanted to check my current glucose readings, where would I look? How would I interpret this?
8. In your opinion, are these different readings easy to understand?
9. When did you notice you were having high alarms? What do you believe could have caused this and why?
10. Were there any changes to your eating habits after wearing the CGM?
11. Were there any changes to your exercise habits after wearing the CGM?
12. What is something you would improve about the CGM experience?
13. What are three of your favorite apps on your phone you use in the past 3 months?
14. What do you like about app X? Is there something you don't like about it?
15. Is there something you learned about this experience
16. Would you recommend this to someone else? Why?
17. Were you able to create a general rule about how glucose is related to diet?

APPENDIX J: G1- Continuing Glucose Monitoring Gift Card Log

Batch # _____

Vendor	Card Seq Number	Amount	Date	Participant ID	Participant's Initial	Participant's Signature	Time Given	Baseline Visit	Post-Visit
Amazon		\$100.00							
Target		\$100.00							
Walmart		\$100.00							

APPENDIX K: PARTICIPANT ACTIVITY LOG

Participant ID	Screening Date	Baseline visit date	Enrolled	If not, why?	Date of sensor replacement	Post visit date	Adverse event	Date of AE	Completed
G1xxx	Mm/dd/yyyy	Mm/dd/yyyy	 Yes  No	Reason	Mm/dd/yyyy	Mm/dd/yyyy	 Yes  No	Mm/dd/yyyy	 Yes  No

APPENDIX M: DEMOGRAPHICS SURVEY

Demographics

Page 1

Please complete the survey below.

Thank you!

Demographic Questionnaire

What is the highest level of education you have completed?

- 8th grade or less
- Some high school
- High school diploma/G.E.D.
- Trade/vocational school
- Some college
- 2-year college - Associate's degree
- 4-year college - Bachelor's degree
- Master's degree
- Doctoral/Professional degree
- Not sure

What is your current marital status?

- Single
- Married
- Divorced
- Separated
- Widowed
- Domestic Partnership
- Other

Please specify your marital status:

What is your current employment status?

- Employed
- Self-employed
- Unemployed
- A homemaker
- A student
- Retired
- Unable to work due to disability

What type of housing do you currently reside in?

- House
- Apartment
- Mobile home
- Hotel
- Shared housing with another family
- Car

11/11/2024 7:49am

projectredcap.org

REDCap®

APPENDIX N: BEVERAGE SURVEY

Page 1

Beverage Survey

Please answer the items below as accurately as possible to calibrate the glucose sensor.

In the last 7 days, how many days did you drink the following drinks (don't include beverages with artificial sugars):

	Never	1 day	2 days	3 days	4 days	5 days	6 days	7 days
1) Water								
2) Fruit juice								
3) Milk								
4) Diet Soda								
5) Regular Soda								
6) Black coffee / tea								
7) Sweetened coffee / tea								
8) Wine/ beer								
9) Energy / sports drinks								

11/11/2024 7:49am

projectredcap.org

APPENDIX O: BEHAVIORS SURVEY

Page 1

Behaviors Survey

Please answer the items below as accurately as possible to calibrate the glucose sensor.

In the last 7 days, on how many days did you:								
	Never	1 day	2 days	3 days	4 days	5 days	6 days	7 days
1) Take Tylenol or aspirin								
2) Take vitamin C (includes multi-vitamins)								
3) Take medicine prescribed by your doctor								
4) Drink one or more servings of alcohol								
5) Smoke cigs, e-cigs, or vape								
6) Do meditation (such as mindfulness, breathwork, mantra)								
7) Do yoga (such as Hatha, hot yoga, Tai Chi)								

11/11/2024 7:49am

projectredcap.org

REDCap®

APPENDIX P: PHYSICAL ACTIVITY IPAQ

Physical activity IPAQ

Page 1

Please complete the survey below.

Thank you!

INTERNATIONAL PHYSICAL ACTIVITY QUESTIONNAIRE

We are interested in finding out about the kinds of physical activities that people do as part of their everyday lives. The questions will ask you about the time you spent being physically active in the last 7 days. Please answer each question even if you do not consider yourself to be an active person. Please think about the activities you do at work, as part of your house and yard work, to get from place to place, and in your spare time for recreation, exercise or sport.

Think about all the vigorous activities that you did in the last 7 days. Vigorous physical activities refer to activities that take hard physical effort and make you breathe much harder than normal. Think only about those physical activities that you did for at least 10 minutes at a time.

1. During the last 7 days, on how many days did you do vigorous physical activities like heavy lifting, digging, aerobics, or fast bicycling?

(days per week)

2. How much time did you usually spend doing vigorous physical activities on one of those days?

Example, if you spent 2.5 hours per day, input 2 as hours per day and 30 as minutes per day. If you spent 1 hour, input 1 hour and 0 minute.

{vighour} hours per day
{vigmin} minutes per day

Think about all the moderate activities that you did in the last 7 days. Moderate activities refer to activities that take moderate physical effort and make you breathe somewhat harder than normal. Think only about those physical activities that you did for at least 10 minutes at a time.

3. During the last 7 days, on how many days did you do moderate physical activities like carrying light loads, bicycling at a regular pace, or doubles tennis?
Do not include walking.

(days per week)

4. How much time did you usually spend doing moderate physical activities on one of those days?

Example, if you spent 2.5 hours per day, input 2 as hours per day and 30 as minutes per day. If you spent 1 hour, input 1 hour or 0 minute.

{modhour} hours per day
{modmin} minutes per day

APPENDIX Q: SENSOR REPLACEMENT CALL SURVEY

Page 3

Did the call take place with the participant? Yes No

Insert the date that the sensor was replaced: _____

Sensor ID code of the replacement sensor: _____

Is the Dexcom Glucose kit complete with all its components? Yes No

How many days have you worn your CGM since we put it on? _____

Have you experienced any problems with your glucose monitoring system (sensor or app)? Yes No

Insert notes for sensor problems, smartphone app problems, and adverse events. _____

Was the sensor successfully replaced? [Have the participant show you their smartphone screen to verify working order] Yes No

En que lugar almaceno su segundo sensor? _____

Insert any additional notes related to this phone interview that impact the participant or data capture. _____

Other notes: _____

Upcoming visit date: _____

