The study staff will then congratulate the participant for successfully applying the sensor and pairing the sensor to their smartphone. After words of encouragement have been given, the staff will then explain to the participant that they will complete daily videos in which they will answer questions that the study staff will send through a text message every day, within those videos they will sincerely share their experience with the Dexcom sensor. The study staff will explain that on the days they obtain “high glucose” alerts, they will create a video describing in what situation the participant was in when the alarm was received; they will describe what foods they ingested before obtaining the alarm as well.

The final step of this procedure involves explaining to participants the signs and symptoms they should report to the research staff regarding the sensor. These include swelling, redness, bruising or bleeding. Participants must notify the research staff if the transmitter falls off or if any errors occur within the app. The study staff will make the remark that the participant cannot remove the sensor unless it is instructed by the study staff. Additionally, participants should be reminded that the transmitter-sensor is effective for 10 consecutive days. Provide each participant with a yellow folder to store the used transmitters. Remind the participant they are to bring their transmitters with them on their return visit.

[figure not shown]
Before the participant puts his/her smartphone away, the study staff will ask the participant if they already have a Zoom App and Zoom account and explain that this app is needed for the sensor replacement video call. If the participant does not have a Zoom account, the study staff will help and guide the participant to download the Zoom app and with the creation of a Zoom account.

Instructions for G6-Pro placement and transmitter attachment

For additional information related to inserting the sensor, please see the Dexcom G6 Pro CGM System User Guide

1BL017544 Rev

1. After the sensor is inserted and the transmitter has been snapped into the sensor pod, open the G6 app and follow prompts to create a username and password. Log in to the app and follow the set-up

wizard. Refer to the unblinded CGM patient handout that is included in your box.

- a. The study staff will keep the adhesive backings of the applicator because this adhesive contains the 4-digit code that will be entered into the receiver/reader.

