The study staff will provide \$100 gift card compensation to all participants attending the baseline interview and complete the protocols. Since this is the last procedure, the participant will be involved with for this visit, the study staff will provide an envelope to the participant. The envelope will be labeled with the name of the study, the research coordinator's name and contact number. In the envelope the participant will locate two Ziploc baggies, 1 for each worn sensor. Each baggie will be labeled as "sensor 1" and "sensor 2;" the baggie will also contain one of the stickers designated for each sensor (these stickers will be found within the Dexcom G6 Pro kit box). The study staff will explain to the participant that the bag labeled "Sensor 1" is for them to put in the sensor that has been recently applied on the 10th day and the bag labeled "Sensor 2" is designated for the 2nd sensor they will apply on their own once they have completed the 20 days (about 3 weeks) of the CGM phase.

Data entry

The study staff will ensure to transfer the baseline data collected from the participant's chart into the RC system on the same day as the baseline visit. This will ensure that the main data capture system remains up to date.

CGM Wear Phase

The CGM wear phase will span 20 consecutive days. Throughout this period, we will gather data from the participants on a weekly basis. The sensor will be replaced once on day 10. Each morning, participants will receive text prompts to log dietary behaviors that triggered high out-of-range alarms; these logs will be recorded directly in the app by the participant. During the Zoom-supported sensor replacement call, the staff will replace the sensor and inquire about any adverse events or serious adverse events related to the sensor. Additionally, study staff will conduct Zoom sessions with participants on the 10th day of wearing transmitters during the CGM phase.

Dietary logs

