The research staff will send a text message to the participant to remind them the date and time they scheduled the sensor replacement 48h before the sensor replacement. The research staff will conduct a Zoom phone call with each participant on day 10 to assist with sensor replacement. The replacement Zoom will be scheduled during the baseline visit. Additionally, participants will be asked about any adverse events related to the CGM sensor as listed on the RC survey form, including inputting AE and SAE. Three days before the scheduled call, the research staff will send each participant a G6-Pro application video tutorial. On the 10th day of wearing the CGM, the research staff will meet with participants via Zoom to guide them through the process of changing the G6-Pro sensor. During this meeting, the research staff will provide a step-by-step explanation of the sensor replacement procedure, allowing participants to ask any questions they may have and receive support from the research team. Participants will be reminded not to discard the used transmitter-sensor; instead, they will be instructed to place it in the envelope provided by the research staff during the baseline visit.

Before the zoom call takes place, the study staff will login into their RC account and select the G1-Study project to be able to access the participants' charts of the G1-Study. After the website takes the staff to the study page, the staff will select the tab called "Record Status Dashboard" found on the left hand of their screen. The platform will then show the list of each participant and with each form/survey involved in each phase of the study. For this activity, the study staff will choose the only survey found on the "CGM Phase" column. The study staff will have this survey open throughout the zoom call and will complete the form after the participant has successfully removed the old sensor and replaced the new G6 PRO sensor. An example of the Sensor Replacement Telephone script is provided in the Appendix _H_.

Compensation

For the CGM phase, each participant will receive \$200 compensation, which will be given as gift cards. The first \$100 gift card is assigned to the first 7-10 days of successful wear, and \$100 is applied to the second 7-10 days of wear after replacement. Both gift cards are given to the participant at their post visit.

Post-Visit

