7. **Physical Activity Survey**: The International Physical Activity Questionnaire (IPAQ) is a self-reported tool designed to assess physical activity levels in adults aged 18-65 years. IPAQ collects information on the frequency, duration, and intensity of physical activities across four domains: work-related activities, transportation-related activities, domestic and household chores, and leisure-time activities, including recreational and sports activities. Participants recall their physical activity behaviors over the past 7 days, reporting the time spent in various activities at different intensity levels: vigorous-intensity activities, moderate-intensity activities, and walking. Total physical activity levels are calculated by summing the duration and frequency of activities across all domains. This assessment will be presented as a self-administered survey completed using the office computer. The survey data will be recorded in the previously mentioned electronic data capture system. A sample of this form can be found in Appendix_P_.

CGM Phase

The sensor wear phase can last up to 20 continuous days. During this phase various forms can be collected. The forms pertaining to this phase are the following:

1. G6 Replacement Call: The research staff will conduct a Zoom phone call with each participant on day 10 to assist with sensor replacement. Before the zoom call takes place, the study staff will login into their RC account and select the G1-Study project to be able to access the participants charts of the G1-Study. Once the study staff has access to the specific participant chart; the study staff will then click on the form labelled "G6 Replacement Call" in the REDcap project. This form collects information regarding date and time in which the Zoom call takes place, if the sensor was removed and replaced by the second sensor. If the sensor was not replaced, the study staff will type the reason in the comment section that prompts out after selecting that the participant did not replace the G6 sensor. The form also collects the transmitter code of the second sensor and contains a section to specify where the participant stored the glucose sensor kit prior to the sensor replacement. A comment section is added at the end of the form in which the study staff will be able to add any other related information or data collected throughout the Zoom call with the participant. A sample of this form can be found in Appendix_Q_.

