2. Adverse Event form: This form will be used in case of any untoward unexpected event is reported by the participants. The events that will be captured in this form are signs or symptoms that the participants report throughout the study, CGM errors that participants present throughout the CGM wear phase including glucose sensor detachment. In cases where a participant reports any symptoms or any CGM related issue, the research staff will reach out to the participant via phone call. During this call, the study staff will ask for details about the errors shown in the Dexcom Apps. The study staff will fill out an Adverse Event/CGM Error form in the RC platform. In this form, the study staff will specify the date and time when the CGM error started and when the error or issue was resolved. This form includes a comment section in which the study staff will type a detailed explanation of the symptoms or issues that the participants express throughout the phone call. Once the issue has been resolved, the study staff will reach out to the PI within 24 hours to report that an AE/CGM error form was completed for a participant and describe the case to the PI. A sample of the form can be found in Appendix_R_.

Post Visit

Different forms will be collected throughout the last visit. These forms will be presented as self-administered surveys and will be completed using the office's computer. The forms administered during this initial visit are the following:

1. Body Measurement Form: This form will be physically completed during baseline and post visits. It contains specific parameters such as weight, height and current medication intake. During the baseline visit, both physical

and electronic CRFs will capture weight and height data. After the participant leaves the Soto building, the study staff will transfer this data to the eCRF.

2. Physical Activity Survey: This assessment will be presented as a self-administered survey completed using the office computer. Details of what this survey entails can be found in page 54.
3. Beverage Survey: This assessment will be presented as a self-administered survey completed using the office computer. Details of what this survey entails can be found in page 54.
4. Behaviors Study: This assessment will be presented as a self-administered survey completed using the office computer. Details of what this survey entails can be found in page 54.

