[Ask the participant if they have inserted the transmitter, if so, ask if the transmitter made a clicking noise]

Now that you have successfully inserted the transmitter, rub the sides of the adhesive with circular motions. Rub it at least 4 times.

Great job Mr./Mrs. _____, you have successfully applied your new sensor. Let’s now start to pair your new sensor with your smartphone. Unlock your smartphone and go into the Dexcom G6 App. Within your App, touch the settings icon found in the upper right-side corner of your screen

[Show on screen to the participant the settings icon of the app].

Now touch the fifth tab called “Transmitter”. You will see a section called “Pair New” on your screen.

[Show once again to the participant on screen the Pair New section]

Select that tab and hit the “continue” tab. The app will give you the option to either enter the Transmitter Code manually or scan the QR code. I’d like you to choose the QR code option. The app will open the camera so you can capture the QR code found on the sheet I mentioned at the beginning containing the sensor’s code.

[Show on screen once again the sheet with the QR code].

After you scan the code, the app will automatically pair your new sensor with your smartphone. The sensor will take up to 2 hours to warm up. After the 2 hours have passed, the G6 app will show you your glucose levels graph.

Amazing job, Mr./Mrs. _____. You successfully replaced and paired your new Dexcom G6 PRO sensor. We will now finish this zoom call with a short survey. Are you okay if we complete this now or do you need to take a 3-minute break?

[Once the participant has accepted to go on with the survey, the staff will go into the RC page that was set up from the beginning of the zoom meeting and will enter the correct data into the RC platform. Within this survey the study staff will schedule the date and time of the Post Visit. After finishing the survey, the staff will answer the participant’s questions and will thank them for their participation]

Thank you so much for participating in this phase of the study. Remember that if you have any problems with your sensor or the Dexcom app, feel free to contact me so I can help you solve the problem.

Before we go, I want to kindly remind you to continue making the daily videoclips so we can capture your entire experience with the glucose sensor."

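### The day-10 call is meant to ask about adverse events listed on its form, but the form page shown lists none and asks participants only about sensor or app problems

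*Protocol*

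**What the plan says.** Two instructions in protocol section 3.13.2 cover adverse events on the day-10 call. Under CGM Wear Phase, staff are to "inquire about any adverse events or serious adverse events related to the sensor". Under G6 sensor replacement, "participants will be asked about any adverse events related to the CGM sensor as listed on the RC survey form".

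Appendix Q reproduces the form. Its question to the participant about problems is "Have you experienced any problems with your glucose monitoring system (sensor or app", with a Yes/No answer. The next line is addressed to staff: "Insert notes for sensor problems, smartphone app problems, and adverse events".

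At baseline (section 3.13.2, CGM application) participants are told which signs concerning the sensor to report: "These include swelling, redness, bruising or bleeding".

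The adverse-event form is described in section 3.17.3: "This form will be used in case of any untoward unexpected event is reported by the participants". SAP section 6.3 takes adverse events from participant report or occasional assessment.

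**The concern.** The protocol sends the caller to a list on the form, and the page shown has no list. What the participant hears is a question about a device. Someone whose sensor reads correctly but whose skin is red or bruised may take that question to be about device function and answer No.

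The safety outcome in SAP 6.3 rests largely on what participants say. The day-10 call is the one scheduled contact at which the protocol explicitly requires an adverse-event inquiry. If the wording of that inquiry is left to the caller, a low count of skin reactions could reflect either few reactions or weak questioning, and the report could not separate the two. The issue is what is asked, not when or how often.

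**Working it through.** This is a check of wording, and the plan gives no figure to reproduce. The places that could supply the question compare as follows.

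- **Instruction (3.13.2, G6 sensor replacement).** Refers to adverse events listed on the form.
- **Instruction (3.13.2, CGM Wear Phase).** Requires an inquiry about adverse and serious adverse events, but gives no wording and names no form.
- **Form (Appendix Q).** Contains no symptom list and no adverse-event question. The participant is also asked how many days the sensor was worn and where the second one was stored. Of the items put to the participant, only the sensor/app item asks about problems. The notes field tells staff where to write an event. It asks the participant nothing.
- **Description of the form (3.17.3, G6 Replacement Call).** Begins "This form collects information regarding date and time in which the Zoom call takes place" and goes on to replacement, the reason if not replaced, transmitter code, storage and comments. No adverse-event item is named.
- **Call script (Appendix H).** Has no symptom or skin question. Its closing invitation keeps the device framing: "if you have any problems with your sensor or the Dexcom app, feel free to contact me".
- **Baseline briefing (3.13.2, CGM application).** Names four signs. Neither the form nor the script repeats them.

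Other contacts could pick up a reaction, but none is an adverse-event inquiry with stated wording:

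- daily texts that check wellbeing on days 1 to 20 (section 3.7);
- general monitoring of side effects at any interaction (section 3.15);
- interview questions on how wearing the device felt and what was disliked (Appendix I);
- agreement-scale items on skin irritation or bruising and on pain in the satisfaction survey (Appendix U).

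The post-visit procedures listed in sections 3.13.2 and 3.13.3 include no adverse-event inquiry.

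**Timing.** Final screening was on August 30, 2024 (section 3.6), and initial visits are scheduled within 7 days (section 3.7). On that schedule the last baseline visit falls by about September 6 and the last day-10 call by about September 16, 2024. Section 3.17.4 describes visits in the past tense. The calls for this cohort have therefore probably been made.

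**Illustration only.** Suppose 20 participants and no recorded events, and let s be the share of true events found by all channels together. The one-sided 95% upper limit for the true proportion p solves (1 − s·p)^20 = 0.05, so p = (1 − 0.05^(1/20))/s = 0.139/s. This gives 13.9% for s = 1, 27.8% for s = 0.5 and 55.6% for s = 0.25. If 20% truly had a reaction, the chance of recording none is (1 − 0.2·s)^20, which is 1.2%, 12.2% and 35.8% for the same three values. The 20% rate and every value of s are assumptions without a source in the documents. The figures show why ascertainment matters to a zero count. They do not measure what this form misses.

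**The case against.** A reader might infer that participants are never asked about adverse events, or that a skin reaction must truthfully be answered No. The documents support neither inference. Section 3.13.2 separately tells staff to inquire about adverse and serious adverse events, and the form has a field in which to record them. What is missing is scripted wording, not the instruction to ask. The baseline briefing also presents skin signs as matters concerning the sensor, so a participant who remembers it may well answer Yes to the sensor/app item. The defensible statement is that No is a possible answer.

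A reader might also infer that anything noted on the call stays in free text outside the adverse-event form. Section 3.17.3 says otherwise: once a participant reports a symptom, staff telephone and complete that form. Appendix Q as shown carries no reminder of this step.

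The evidence on the form is also incomplete. The Appendix Q page is numbered 3, and the reason field described in section 3.17.3 for a sensor that was not replaced is not visible on it. An adverse-event item could exist elsewhere in the form, although the protocol's own description mentions none. The script hands over to the survey before the call closes, so its silence alone is weak evidence.

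Finally, this is a 20-person pilot whose SAP plans no inference on adverse-event rates, and other channels touch on skin and comfort. That limits the consequences. It does not remove the mismatch between an instruction that cites a list and a form page that has none.

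**Conclusion.** The point holds in a limited form. On the page shown, the day-10 form does not contain the list of adverse events the protocol says it contains, and its one problem question to the participant is about the sensor or app. Eliciting a skin reaction under a working sensor is left to unscripted inquiry, to volunteering, or to channels that are not adverse-event records.

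The size of any under-recording is unknown, and nothing in the documents allows it to be estimated. The conclusion assumes that the reproduced page and the description in section 3.17.3 together represent the form. If an unseen page carries a symptom list, what remains is to show it in Appendix Q. The change is inexpensive and worth making. It does not affect the primary glucose analysis.

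**What to change.** 1. Reconcile the two instructions in section 3.13.2 with Appendix H and Appendix Q. On the form, apart from the sensor/app item, add Yes/No questions to the participant for swelling, redness, bruising and bleeding, which the baseline briefing already names. Add one item on any other symptom or medical event since the sensor was placed.
2. State on the form that each Yes triggers the adverse-event form described in section 3.17.3.
3. In SAP 6.3, tabulate from these Yes/No items together with the adverse-event forms. Appendix R alone would not give categories: apart from dates, a device-related Yes/No and a broad outcome item, it describes the event in free text.
4. For participants whose call has already taken place, compare the Appendix Q notes with the Appendix R records, resolve any event that appears in only one, and state in the report that events were elicited without a scripted symptom question. The revised form then serves the subsequent study foreseen in SAP section 2.1.

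The cost is about five REDCap items and about a minute per call. Prompted questions will raise the recorded count, so later results will look less favourable than, and will not be directly comparable with, those collected without prompts.
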